9.3 Endpoint Adjudication Committee

- ✓ The adjudication committee's role is to analyze patient data in detail and conclude whether the event (endpoint) is present or not. The committee will therefore be made up of specialists in the pathology or endpoint of the trial. It is not necessarily independent of the trial, but the main thing is that it acts blindly. There is therefore a lot of preparatory work to provide the committee with anonymized and undated data.
 - Members of the committee: [name], [name], [name], [name]
 - Missions: Secondary endpoints adjudication
 - Operating methods: Meetings when 25, 50, 75 and 100% of the patients are monitored.
- ✓ Outcomes concerned :
Secondary endpoints adjudication
- ✓ Primacy of the opinion of the adjudication committee:
The adjudicated outcome takes precedence over that of the investigator

10 SAFETY ASSESSMENT - RISKS AND RESTRICTIONS ADDED BY THE RESEARCH

10.1 Description of parameters for assessing safety

SmPC will describe more detailed information on the known and anticipated risks and reasonably expected adverse events (AEs) of cilostazol.

10.2 Anticipated methods and timetable for measuring, collecting and analysing the parameters for assessing safety

The Investigator is responsible for the detection and documentation of events meeting the criteria and definition of an AE or SAE, as provided in this protocol. During the study when there is a safety evaluation, the Investigator or site staff will be responsible for detecting, documenting and reporting AEs and SAEs as detailed in this Section of the protocol.

10.3 Procedures in place for recording and reporting adverse events

Adverse events will be collected by physicians in charge on a daily basis, and reported through an e-CRF by investigators. They will be classified as mild, moderate or serious adverse events.

10.3.1 Definitions (Regulation (EU) N° 536/2014 (REC)

Adverse event Any untoward medical occurrence in a patient or clinical trial subject administered a medicinal product and which does not necessarily have a causal relationship with this treatment.

- **Adverse drug reaction**

Any response to a medicinal product which is noxious and unintended.

- **Serious adverse event**

Any untoward medical occurrence that at any dose results in death, is life-threatening, requires inpatient hospitalisation or prolongation of existing hospitalisation, results in persistent or significant disability/incapacity, or is a congenital anomaly/birth defect.

- **Unexpected adverse reaction**

An adverse reaction, the nature, severity or outcome of which is not consistent with the applicable product information: the summary of product characteristics (SmPC) for an authorised product or the investigator's brochure for an unauthorised investigational product.

According to the notice to sponsors of clinical trials for medications (ANSM):

- **New safety issue**

Any new information regarding safety:

- that could significantly alter the assessment of the benefit-risk ratio for the experimental medication, or for the trial
- or which could lead to the possibility of altering the administration of the experimental medication or altering the conduct of the trial

Examples:

- a) any clinically significant increase in the frequency of an expected serious adverse reaction occurring
- b) suspected unexpected serious adverse reactions (SUSAR) occurring in patients who have finished the trial and about whom the sponsor is notified by the investigator, who also provides any follow-up reports
- c) any new fact relating to the conduct of the clinical trial or the development of the experimental medication, if the new fact is likely to affect participant safety

Examples:

- a serious adverse event likely to be related to the investigations and to the trial's diagnostic procedures and which could modify the conduct of this trial
- a significant risk for the trial participants such as ineffectiveness of the experimental medication used in the trial in treating a life-threatening illness
- significant safety results from a recently completed research carried out on animals (such as a carcinogenicity research)
- the premature termination, or temporary interruption, of a trial conducted with the same experimental medication in another country, for safety reasons

- an unexpected serious adverse reaction associated with a non-experimental medication required for carrying out the trial, (e.g., challenge agents, rescue treatment)
- d) recommendations from the data safety monitoring board (DSMB), if applicable, if they are relevant to the safety of the participants
- e) any unexpected serious adverse reaction reported to the sponsor by another sponsor of a trial carried out in a different country but relating to the same medication

10.3.2 The investigator's roles

10.3.2.1 Regulatory obligations of the investigator

The investigator must notify the sponsor, **immediately on the day when the investigator becomes aware**, of all the serious adverse events, except those that are listed in the protocol (see. section 10.3.3.1) or in the investigator's brochure as not requiring immediate notification.

These serious adverse events are recorded in the "adverse event" section of the case report form and the investigator must immediately notify the sponsor's Vigilance division (see 10.3.4).

10.3.2.2 The investigator's other roles

The investigator must document the serious adverse event as thoroughly as possible and provide the medical diagnosis, if possible.

The investigator assesses the severity of the adverse events by using an adverse events rating scale, attached to the protocol, by using general terms:

- *Mild: tolerated by the patient, does not interfere with daily activities*
- *Moderate: sufficiently uncomfortable to affect daily activities*
- *Serious: preventing daily activities*

The investigator assesses the causal relationship between the serious adverse events and the experimental medication(s) added by the research.

10.3.3 Specific features of the protocol

All serious and non-serious adverse events must be reported in the CRF.

10.3.3.1 Serious adverse events that do not require the investigator to immediately notify the sponsor

These serious adverse events are only recorded in the "adverse event" section of the case report form.

- **Normal and natural evolution of the pathology:**

Normal and natural evolution of aneurismal SAH is quite variable:

- Even without initial neurological deficit, patients are closely monitored after securisation of the aneurism because of the risk of DCI, vasospasm, hydrocephalus, rebleeding, or any other unspecific complication. Patients in worse neurological condition can be initially intubated; the duration of mechanical ventilation dependst on the subsequent neurological improvement and intercurrent ICU complications.
- Securisation of the aneurism can be performed with endovascular coiling or surgical clipping and lead to ischemic stroke

- Death occurs in approximately 30% of all cases.
- DCI can occur from day 4 until the 21th day after SAH. This risk peaks about the 10th day. DCI can require hypertension therapy and infusion of vasopressor, adjunctive pharmacological treatment, notably milrinone, and endovascular treatment of vasospasm can be requested, but in a centre-dependant way
- Other organ failure might occur as patients might require prolonged ventilatory support and developed ICU related complications, such as nosocomial infection.
- Initial hydrocephalus can worsen the neurological status; it can occur from the first to 15th day. It can require an external ventricular drain. The drain can often be weaned during hospitalisation but if not, internal ventricular drainage can be implanted. It is associated with a risk of nosocomial menigitis.
- When the risk of DCI or other neurological complication is considered low enough, the patient is transferred to the ward until the patient is discharged from the hospital to either the patient's home or a rehabilitation centre.
- **Adverse events likely to be associated with the treatments prescribed as part of the patient's care during the monitoring of the research**

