10.3.3.2 Serious adverse events that require the investigator to immediately notify the sponsor

The investigator must report all adverse events that meet one of the seriousness criteria below, except for events listed in section 10.3.3.1 as not requiring notification:

- 1- Death
- 2- Life threatening situation
- 3- Requiring hospitalisation or prolonging hospitalisation
- 4- Persistent or significant disability or incapacity
- 5- Congenital abnormality or birth defect
- 6- Or any other adverse event considered "medically significant"

- ❖ For serious adverse events related to the experimental medication(s) and which are expected:
 - the -SmPC for the « **cilostazol** » speciality, found in (Appendix 5), should be consulted.
- ❖ The serious adverse events associated with specific research procedures or exams, and which are expected, are:
 - Poorly tolerated auricular or ventricular arrhythmia
 - Abnormal bleeding (requiring blood transfusion or not)
 - Allergy

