10.3.3.3 Other events that require the investigator to immediately notify the sponsor

- **Adverse events that are "not serious" but which are significant for the safety of participants**
- The following adverse event will be assessed:
 - Well tolerated arrhythmia from auricular origin
 - Well tolerated arrhythmia from ventricular origin
 - Tachycardia,
 - Fever
 - Fainting

- Nausea
- Vomiting
- Stomach pain
- The investigator must notify the sponsor about these "nonserious" adverse events, in accordance with the same procedures and deadlines as serious adverse events (see section 10.3.4). These events can be considered "medically significant".
- **In utero exposure**

The sponsor must be notified immediately about any pregnancy during which the foetus (from the pre-embryonic stage up to birth) could have been exposed at a given time to an experimental medication, even if the pregnancy is not associated with an adverse event.

Notification is required if the exposure involves:

- the mother,
- the father if the experimental medication is genotoxic.

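### The natural-evolution exemption in section 10.3.3.1 leaves it unclear whether a serious rebleed, or a death possibly related to study drug, must be notified immediately

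*Protocol*

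**What the plan says.** Section 10.3.2.1 requires the investigator to notify the sponsor of every SAE on the day of becoming aware of it, "except those that are listed in the protocol (see. section 10.3.3.1") or in the investigator's brochure.

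Section 10.3.3.1 is that list. Its opening line gives the consequence of being on it: "These serious adverse events are only recorded in the" adverse event part of the CRF. The first exempt category is the normal and natural evolution of the disease, described in a series of bullets. One explains that "patients are closely monitored after securisation of the aneurism because of the risk of DCI, vasospasm, hydrocephalus, rebleeding, or any other unspecific complication". Another reads "Death occurs in approximately 30% of all cases". Neither is limited by cause, by timing, or by suspected relation to study drug.

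Section 10.3.3.2 covers SAEs that do need immediate notice. Death is its first seriousness criterion, and the rule applies "except for events listed in section 10.3.3.1 as not requiring notification". The same section names, among expected SAEs, "Abnormal bleeding (requiring blood transfusion or not").

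Section 10.3.3.3 adds non-serious events, including nausea, vomiting and fever, to be notified "in accordance with the same procedures and deadlines as serious adverse events". Section 10.3.5 sets the reporting period and asks for all SAEs, with no exception stated.

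**The concern.** Exempting expected disease events from same-day notice is a common and defensible choice. It becomes a problem when the exempt description overlaps a named risk of the drug under test. Section 2.5 describes cilostazol as an antiplatelet agent, and section 4.1.2 lists abnormal bleeding as a cilostazol-related major adverse event. Rebleeding is the bleed most closely tied to the disease, and it is named in the exempt text.

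Under section 4.2.5 the treating staff are blinded, so an investigator facing a rebleed cannot use the allocation to judge whether the drug contributed. Classifying it as natural evolution is then the easy course. The open-ended final category in the same bullet could absorb almost any other complication.

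At stake is how early the sponsor learns of serious bleeding. Under section 10.3.6.1 the sponsor assesses causality and declares unexpected serious reactions. Under section 5.8.4 a difference between arms in serious adverse reactions is a ground for stopping. Both work better with prompt notice.

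**Working it through.** No arithmetic decides this point. The check is to set the sections side by side and follow particular events through them.

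**The rules**

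1. Section 10.3.2.1: same-day notice of all SAEs, less those in 10.3.3.1.
2. Section 10.3.3.1: CRF entry only. The text names rebleeding, an open-ended remainder, and death.
3. Section 10.3.3.2: immediate notice of events meeting a seriousness criterion (death first), less those in 10.3.3.1. Abnormal bleeding is named within this section.
4. Section 10.3.3.3: listed non-serious events follow SAE deadlines.
5. Section 10.3.4: after the initial notification, a follow-up report is due within 8 days for a fatal or life-threatening event.
6. Section 10.3.5: all SAEs are to be reported, with no exception stated.

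**Event A: a serious intracranial rebleed during the 14 days of treatment.** Read through rule 2, it is natural evolution and goes in the CRF only. Read through rule 3, it is abnormal bleeding and is notified immediately. Read through rule 6, it is reported. No sentence gives one reading precedence.

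**Event B: a death.** Rules 1 and 3 both carry the exception, so they agree with each other: a death from natural evolution is exempt. What is missing is the treatment of a death in which the drug may have played a part. The heading of the category suggests that such a death is not natural evolution, but no sentence says so. Rule 5 presupposes an initial notification that rule 2 may have removed.

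**Event C: non-serious nausea.** Rule 4 requires notice on SAE deadlines, with no exemption.

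The result is that event C is always notified promptly, event A may or may not be, and event B depends on a judgement for which the protocol gives no criterion.

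**Is rebleeding picked up by another route?** Section 5.1 collects recurrent bleeding, but only at inclusion. Daily follow-up in section 5.2 has an item for abnormal bleeding, which would capture a rebleed if the investigator regards it as such. The efficacy criteria in section 4.1.2 include delayed cerebral ischaemia, vasospasm and new infarcts, but not rebleeding by name.

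**The case against.** The strongest reply is that section 10.3.3.1 is a narrative of the disease and not a list of exempt events. Death appears as an incidence statement and rebleeding as a reason for monitoring; another bullet describes transfer to the ward, which is no adverse event at all. On the heading's own words, a bleed thought to come from the drug is not natural evolution. Section 10.3.2.2 has the investigator assess causality for SAEs, and section 10.3.5 can be read as setting the time window rather than the scope. This is a reasonable reading and probably the intended one. It does not remove the fault, because investigators must infer the exemption from prose, and the prose is open-ended.

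Second, the abnormal-bleeding entry in section 10.3.3.2 sits in a list of expected events tied to research procedures or exams. It is not a separate notification rule. That stands: the duty to notify follows only from its place in that section, which is part of the ambiguity.

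Third, exempt events are not lost. Section 10.3 has adverse events collected daily and reported in the e-CRF, section 13.1.2 monitors safety data at 100%, and section 10.3.7 lets the safety board set how SAEs are notified to it. That stands too, and it limits the harm to delay.

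Two stronger readings are tempting and are not supported.

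- A reader might infer that the protocol contradicts itself on death. It does not, because the exception is written into both notification rules.
- A reader might apply the 30% death rate to the sample size, 0.30 × 630 = 189, and conclude that about 190 deaths would escape immediate notice. The rate refers to all cases of the disease, whereas section 12.5 says the trial leaves out early deaths and patients without surgery. The design rates (65% and 76% favourable, 315 per arm) imply 0.35 × 315 + 0.24 × 315 = 110.25 + 75.6, about 186 unfavourable outcomes in total, including survivors with mRS 3 to 5. A count of 189 deaths exceeds that total, and it also assumes that every death is classed as exempt.

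**Conclusion.** The concern holds as an over-broad and ambiguous exemption. A serious rebleed in this blinded antiplatelet trial can be read as exempt or as notifiable, and no text says that a suspected relation to study drug overrides the exemption, for bleeding or for death.

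The consequence is possible delay in notice to the sponsor, not loss of data. The documents give no basis for counting the events affected: they state neither a rebleeding rate nor a death rate for this secured-aneurysm population, and they do not show how investigators would classify events. A delay to the safety board is possible but not demonstrated, since the board may arrange its own reporting.

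The conclusion assumes that an investigator would take the natural-evolution narrative as defining what is exempt, which is what the section's heading and opening line invite. Correction is worthwhile because the overlap is with the drug's own named major risk and the change is small.

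**What to change.** Reconcile sections 10.3.2.1, 10.3.3.1, 10.3.3.2 and 10.3.5:

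- State in 10.3.3.1 that the exemption does not cover rebleeding or other serious bleeding, nor any SAE, including death, that may be related to study drug.
- Replace the narrative's open-ended category with an itemised list of exempt events. The description of the disease course can stay as background, marked as such.
- Have 10.3.2.1 and 10.3.3.2 refer to that limited list, and have 10.3.5 say whether its reporting duty is subject to it.

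The cost is a wording amendment and a modest number of additional SAE forms. Immediate notice of every death regardless of cause would be a further step with a larger burden. It is a choice for the sponsor and is not needed to resolve this point.

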5.7 Distinction between care and research

TABLE: Distinction between procedures associated with "care" and procedures added because of the "research "

Procedures and treatments carried out as part of the research	Procedures and treatments associated with care	Procedures and treatments added because of the research
Treatments	DCI and vasospasm preventive and curative treatments (must include nimodipine administration)	Cilostazol or placebo administration during 14 days
Consultations	Routine visits from the physician in charge	Face to face interview at 6 months

Blood samples	Left to the discretion of the physician	None
Imaging, etc.	Imaging (CT scan, MRI, TCD) left to the discretion of the physician	All the imaging techniques evaluating secondary objectives are routinely realized

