7 TREATMENT ADMINISTERED TO RESEARCH PARTICIPANTS

7.1 Description of the experimental medication or medications

7.1.1 Experimental medication 1

Cilostazol 100mg tablets

Packaging type : blisters

Two times a day (every 12 hours) for 14 days, 28 tablets in total

Storage: room temperature

Shelf life: 3 years

Oral form if patient is able to swallow the tablet. If not, tablets will be crushed by the nurse in charge of the patient, and given by oral or enteral route through feeding tube if required. Of note administration of crushed tablet will be standardized at specific timing in each center. In case a patient can eat a meal, the delay between administration and meal will be of 30 minutes minimum

Of note a market authorization (Autorisation de Mise sur le Marché) is available in France for cilostazol in chronic arteritis but no marketed anymore since 2010 in France. The GHU Paris Psychiatry and Neurosciences pharmacy will import cilostazol which is also marketed in Europe. The blinding as well as the creation of a placebo will be subcontracted to a competent GMP establishment. The logistic will be centralized by the pharmacy of the GHU Paris and the pharmaceutical circuit will be co-constructed between GHU Paris and pharmacies of the different investigator centres (storage and delivery).

7.2 Description of the non-experimental treatment or treatments (medications required for carrying out the research)

7.2.1 Non-experimental medication 1

As recommended by French and European guidelines, a preventive medication of DCI by nimodipine has to be administered during the ICU stay. The posology, route (IV or enteral) and length of treatment is left to the discretion of the caring physician.

7.3 Description of the traceability elements that accompany the experimental medication or medications

Designated pharmacists responsible for the receipt, handling and dispensing of study drugs (active and placebo) will maintain study drug records during the study: details of how all phases of dispensing and withdrawal of unadministered drugs will be monitored and controlled, and the patient code/kit code correspondence will be described in the Pharmacy Manual to be established prior to the start of the study.

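### Section 10.3.3.1 exempts SAEs attributed to usual-care treatment from immediate notification without requiring that a study-drug contribution be ruled out, which can delay the sponsor's causality review, including for reactions to the mandatory nimodipine

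*Protocol*

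**What the plan says.** Section 10.3.3.1 is headed "Serious adverse events that do not require the investigator to immediately notify the sponsor". Of the events it lists it says "These serious adverse events are only recorded in the" adverse-event part of the CRF. There are two categories. The first is the natural course of aneurysmal haemorrhage, described broadly: it takes in rebleeding, organ failure, death and complications that are not further specified. The second is a single line with no qualification: "Adverse events likely to be associated with the treatments prescribed as part of the patient's care during the monitoring of the research".

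Two other sections yield to this list. The investigator's general duty to notify on the day of awareness (10.3.2.1) applies to all SAEs "except those that are listed in the protocol (see. section 10.3.3.1") or in the investigator's brochure. The duty based on seriousness criteria, which start with death and life-threatening situations (10.3.3.2), applies "except for events listed in section 10.3.3.1 as not requiring notification".

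Nimodipine appears on both sides of the line between care and research. The table in section 5.7 puts in its care column "DCI and vasospasm preventive and curative treatments (must include nimodipine administration"). Section 7.2 lists it among the non-experimental medicines that the research needs, and 7.2.1 says that "a preventive medication of DCI by nimodipine has to be administered during the ICU stay". Section 10.3.1 gives as an example of a new safety issue "an unexpected serious adverse reaction associated with a non-experimental medication required for carrying out the trial", and 10.3.6.2 gives the sponsor 15 calendar days from its own awareness to declare new facts to the authorities.

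**The concern.** The trial tests cilostazol added to nimodipine. Section 2.3 says no earlier study has evaluated this combination in a large cohort, and section 4.2.1 sets out to show that it is safe as well as superior. Harm from the combination is therefore something that safety reporting has to detect.

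Under the last item of 10.3.3.1, the blinded investigator's view that an event is likely due to care is enough to stop immediate notification. Likely due to care does not mean due to care alone: the same event may also have cilostazol as a plausible cause. Because nimodipine is mandatory, a care treatment is available as an explanation in every patient, and section 7.4 also authorises milrinone and vasopressors. What is at stake is how soon the sponsor can give the second opinion on causality that section 10.3.6.1 asks of it.

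**Working it through.** No calculation applies. The check sets the reporting rules side by side.

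1. **Scope of the exemption.** The last item of 10.3.3.1 has one test: the event is likely associated with a treatment given as care. It does not separate expected from unexpected reactions, or nimodipine from other care, and it does not address events plausibly due to both care and study drug.

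2. **Precedence.** Sections 10.3.2.1 and 10.3.3.2 both make an exception for the list. An SAE that meets the test is therefore CRF-only whatever its seriousness.

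3. **Nimodipine.** Section 5.7 makes it care, so an SAE attributed to it meets the test. Section 7.2 makes it a medicine the research needs, so an unexpected serious reaction to it is an example of a new safety issue under 10.3.1. The declaration duty in 10.3.6.2 belongs to the sponsor and runs from the sponsor's awareness. Section 10.3.1 attaches this kind of new fact to a likely effect on participant safety. Both rules can be followed together, but the exemption removes the quick way for the sponsor to become aware.

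4. **Causality review.** Section 10.3.2.2 asks the investigator about causality with the experimental medication only. Section 10.3.6.1 asks the sponsor to consider the experimental medication and other possible treatments, and counts an event as a suspected reaction if either party thinks a causal link reasonable. It also asks for the first declaration of a suspected unexpected serious reaction without delay after the event occurs. If the sponsor comes to a different view only after finding the event in the CRF, that interval has already passed.

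5. **The arrhythmia rules compared.**

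| Event | Section | Route |
|---|---|---|
| Well-tolerated atrial or ventricular arrhythmia, tachycardia, fainting (non-serious) | 10.3.3.3 | Notified on SAE procedures and deadlines; no exception for the 10.3.3.1 list |
| Poorly tolerated arrhythmia, not attributed to care | 10.3.3.2 | Notified immediately |
| Serious arrhythmia judged likely due to milrinone or a vasopressor | 10.3.3.1, through the exception in 10.3.3.2 | CRF only |

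The milder event is notified faster than the serious one. Yet arrhythmia, abnormal bleeding and allergy are the major cilostazol-related events named in sections 4.1.2 and 5.2.

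6. **What still catches the event.** Adverse events are collected daily and entered in the e-CRF (10.3), the clinical research associate can view entries remotely (13.3), and safety data are monitored at 100% (13.1.2). None of these sections sets a deadline for medical review of a CRF-only SAE.

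**The case against.** The strongest reply is that the sections can be read together sensibly. Section 10.3.3.2 names poorly tolerated arrhythmia, abnormal bleeding and allergy in the part on immediate notification. Section 10.3.3.3 demands prompt notice of even tolerated arrhythmia. An event for which study drug is an equally good explanation is not clearly likely due to care, and the investigator must assess causality with the study drug in any case. Section 10.3.5, on the notification period, speaks of all SAEs. This probably describes what the authors intended. It does not settle the matter, because 10.3.3.2 is expressly subject to the list, 10.3.5 sets a period and does not say that it overrides the list, and no section says that a possible study-drug contribution removes an event from the exemption.

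Three stronger readings are tempting, and the documents do not support them.

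- A reader might infer that 10.3.3.1 and the duty to declare new safety issues contradict each other. They bind different parties, and the sponsor's duty is conditional and starts from its own awareness.
- A reader might infer that the sponsor cannot assess causality for these events. The e-CRF, remote viewing and full monitoring of safety data mean that it can, though possibly late. Nor is it established that the monitoring board would see events late, since section 10.3.7 leaves the method and format of SAE notification to the board.
- A reader might size the problem by applying the DCI rate of about 30% in section 2.2 to the planned sample: 630 × 0.30 = 189. That rate is for survivors, section 10.3.3.1 says only that DCI can require added treatment and that this depends on the centre, and the product counts patients exposed to care, not misrouted SAEs.

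**Conclusion.** The concern holds as a reporting rule that works badly as written. SAEs attributed to care, including unexpected serious reactions to nimodipine and serious arrhythmias attributed to milrinone or vasopressors, are CRF-only without any judgement that cilostazol played no reasonably possible part. The consequence is delay in the sponsor's causality review; the event itself is still recorded and monitored.

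The size cannot be stated as a number of events, because the documents give no rate of SAEs attributed to care. The reach is the whole trial: nimodipine is mandatory, so a care explanation is available for all 630 planned patients. The conclusion assumes that sites follow the text literally and that no other document sets a deadline for reviewing CRF-only SAEs.

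**What to change.** Amend section 10.3.3.1 so that the whole list, both the natural-course category and the care-treatment category, covers only SAEs for which a contribution of study drug is judged not reasonably possible. State in the same place that serious arrhythmia, abnormal bleeding, allergy and unexpected serious reactions to nimodipine are always notified immediately under 10.3.3.2. Changing the last item alone would not be enough: rebleeding and unspecified complications sit in the first category, so a serious bleed could still be CRF-only.

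The amendment should reconcile sections 5.7, 7.2, 10.3.1, 10.3.2.1, 10.3.3.1 to 10.3.3.3 and 10.3.6.2, so that nimodipine's status for safety reporting is the same throughout. It changes no treatment and no analysis. The cost is a sentence or two in an amendment and some additional SAE forms for sites and the vigilance unit. SAEs due to care or to the natural course of the disease, with no reasonable link to study drug and outside the named events, stay exempt.
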